5.1.2. Data Analysis

Unit body weight dose (IU/kg) for analysis of dosing will be calculated as the total IU (nominal dose) for each injection divided by the subject's most recent weight in kilograms prior to the dose of study drug.

Summaries on change from baseline by study visit will be based on subjects who have both study 8HA01EXT baseline and post-baseline values at the visit being summarized. Each of the post-baseline timepoint summaries will contain a row that provides the mean baseline value for the subjects included in that visit summary. There will also be a row for the baseline median where indicated on the table shells.

5.1.3. Handling of Missing Data

Aside from the following, no imputation of study data will be performed.

- The episodic treatment regimen at the start of study 8HA01EXT will be imputed for the scenario specified in Section 5.3.1.
- The end of PK period of the parent study (997HA307 or 997HA309) and start of study 8HA01EXT will be imputed for the scenario specified in Section 5.3.1.
- The occurrence of a new bleeding episode will be imputed if >72 hours lapse between 2 consecutive injections administered to treat a bleed. Details are provided in Section 7.1.1.

For CHO-KLAT, if a subject has data missing at a particular visit, the total score can still be estimated provided at least 27 of the 35 questions have been answered. If a subject's data cannot be used to calculate an overall score that subject will also be excluded from summaries of individual domains at that visit and will be flagged as excluded from summaries in analysis dataset. Details are provided in Section 7.5.3 and Appendix E.

For HAEMO-QoL and HAEM-A-QoL, Hemo-Sat, EQ-5D-Y and EQ-5D-3L, if a subject has data missing at a particular visit for a domain, the total score and subscores will still be estimated provided the questionnaire makes provision for missing domains in the calculation algorithm of overall score. If a subject's data cannot be used to calculate an overall score that subject will also be excluded from summaries of individual domains at that visit and will be flagged as excluded from summaries in data listings. Details are provided in Sections 7.5.1, 7.5.2, 7.5.4 and 7.5.5 Appendix C, F, G, and D, respectively.

For the analysis of AEs and concomitant medications/procedures, if the stop/start date of an AE/concomitant medication is missing or partial, the corresponding study day will be left blank. However, inferences will be made from the partial and missing dates to classify medications as concomitant, AEs as treatment emergent (or not) and AEs during surgical/rehabilitation period. These inferences are described in Sections 6.4.1 and 8.2, respectively.

5.2. Data Summaries

5.2.1. Continuous Variables

Continuous variables will be summarized using descriptive statistics including the number of non-missing values (n), mean, standard deviation (SD), median, minimum, and maximum.

Where specified in the table shells, the 25th and 75th percentiles will also be provided. Means, medians, and the 25th and 75th percentiles will be presented to one decimal place beyond that with which the data was captured. SDs will be presented to two decimal places beyond that with which the data was captured. Minimum and maximum will be displayed to the same number of decimal places as that with which the data was captured.

Unless impractical within a given table, statistics will be aligned by the decimal place in the summary tables (even though not necessarily displayed in this manner in the table shells).

5.2.2. Categorical Variables

Categorical variables will be summarized by counts and percentages. All percentages will be rounded to one decimal place. The percentage will be suppressed when the count is zero. Unless specified otherwise, the denominator for all percentages will be the number of subjects (or other experimental unit, e.g. bleeding episodes) in each treatment regimen or overall with non-missing data for a given summarization. This number (n) will be included with categorical summaries unless the same variable is also being summarized with descriptive statistics, in which case 'n' will already be provided.

5.3. Study Periods

5.3.1. Treatment Regimens for Analysis

For the purpose of analysis, the treatment regimen in study 8HA01EXT means the actual treatment regimen(s) that subjects follow over the course of the study (i.e., not necessarily the regimen they started on). For example, a subject who starts the study on the tailored prophylaxis regimen and switches to the weekly prophylaxis regimen will appear in both the tailored prophylaxis and weekly prophylaxis regimens in the summaries based on the time he spent in the respective regimens.

Start and End of Treatment Regimens

At the start of study 8HA01EXT, the start date and time of the starting treatment regimen is 8HA01EXT Study Day 1 with starting time defined below:

For 8HA01EXT subjects with no gap or a gap of less than or equal to 7 or 4 days:

In general, starting time is defined as either 1) 1 minute after the last rFVIII Fc dose on 8HA01EXT Study Day 1 for subjects on a prophylactic regimen in study 997HA301, 8HA02PED, 997HA307, or 997HA309, or 2) 23:59 on 8HA01EXT Study Day 1 for subjects on the episodic regimen in study 997HA301/997HA307 or subjects who ended the study in a surgical/rehabilitation period in study 997HA301, 8HA02PED, 997HA307, or 997HA309.

For subjects from study 997HA307/997HA309 who only had PK injections (i.e. no injections in treatment phase) and enroll in 8HA01EXT on a prophylactic regimen, the start time is either 1) the time of the prophylactic dose on Study Day 1, or 2) 23:59 on Study Day 1 if there is no prophylactic dose on Study Day 1. The time between 23:59 and 1 minute before the first prophylactic dose in study 8HA01EXT will be imputed as PK period.

For 8HA01EXT subjects with a gap of greater than 7 or 4 days:

Start time is defined as either 1) time of the first rFVIII Fc dose on 8HA01EXT Study Day 1 for subjects on a prophylactic regimen at the start of study 8HA01EXT, or 2) 00:01 on 8HA01EXT Study Day 1 for subjects starting study 8HA01EXT on the episodic regimen or in a surgical/rehabilitation period.

The above definition of the start date and time of the starting treatment regimen is applicable for all subjects with the following exceptions:

- For subjects who were on the episodic treatment arm in study 997HA301 or 997HA307, or only had PK injections in study 997HA307 or 997HA309, and started study 8HA01EXT on the episodic regimen, if there was any dose on 8HA01EXT Study Day 1, then the episodic treatment regimen in study 8HA01EXT will start at the time of that dose.
- For subjects who were on the episodic treatment arm in study 997HA301 or 997HA307 and switched to a prophylactic regimen at study 8HA01EXT start, and had a gap of less than 7 days:
 - If there was no prophylactic dose on the last non-safety follow-up study visit, then the prophylactic treatment regimen in study 8HA01EXT will start at the time of the first prophylactic dose in study 8HA01EXT. The interval from the starting time on 8HA01EXT Study Day 1 (i.e., 23:59 on the day of the last non-safety follow-up study visit) through 1 minute before the first prophylactic dose in study 8HA01EXT will be imputed as the episodic treatment regimen in study 8HA01EXT.
 - If there was a prophylactic dose on the last non-safety follow-up study visit, then the start of the prophylactic regimen in study 8HA01EXT will be the time of that prophylactic dose. In this case, the time from the start of the prophylactic regimen to 23:59 on that day, i.e. the end of the episodic regimen in studies 997HA301 and 997HA307, will be attributed to both study 997HA301/997HA307 and study 8HA01EXT. If there were bleeding episodes during this overlap of time, they would have been attributed to studies 997HA301 and 997HA307.

The end of the last treatment regimen (for subjects who have not changed treatment regimens, it will be the same treatment regimen as they started) will be either 1) the date and time of the last rFVIII Fc dose for subjects whose last treatment regimen was prophylactic or if they were in a surgical/rehabilitation period in study 8HA01EXT, or 2) 23:59 on the day of the last non-safety follow-up study visit for subjects whose last treatment regimen in study 8HA01EXT was episodic.

Treatment Regimen Changes

During study 8HA01EXT, when a treatment regimen changes, the date of the prescribed change will be recorded on the 'Treatment Regimen Assignment Change Details (TRS2)' form in the eCRF. In the following sections, new treatment regimen refers to the one that the subject was changed to, and the previous treatment regimen refers to the one immediately before the new treatment regimen. The start date and time of the new treatment regimen and the end date and time of the previous treatment regimen are defined in the following three scenarios:

- From one prophylactic regimen to a new prophylactic regimen, the new prophylactic regimen starts at the date and time of the first prophylactic dose in the new prophylactic regimen. The previous prophylactic regimen ends 1 minute before that. If the time of the first prophylactic dose in the new prophylactic regimen is not available, the new prophylactic regimen will start at 00:01 on the day of the first prophylactic dose in the new prophylactic regimen, and the previous prophylactic regimen will end at 23:59 on the day prior to that.
- From the episodic regimen to a prophylactic regimen, the prophylactic regimen starts at the date and time of the first prophylactic dose in the prophylactic regimen. The episodic regimen ends 1 minute before that. If the time of the first prophylactic dose in the prophylactic regimen is not available, the prophylactic regimen will start at 00:01 on the day of the first prophylactic dose in the prophylactic regimen, and the episodic regimen will end at 23:59 on the day prior to that.
- From a prophylactic regimen to the episodic regimen, if there is no prophylactic dose on the day of treatment regimen change recorded in the eCRF, the episodic regimen starts at 00:01 on the day of treatment regimen change, and the prophylactic regimen ends at 23:59 on the day prior to the day of treatment regimen change. If there is a prophylactic dose on the day of treatment regimen change, the episodic regimen starts 1 minute after that prophylactic dose, and the prophylactic regimen ends on the date and time of that prophylactic dose.

Duration of a Treatment Regimen

The duration of a given treatment regimen is the time period from the start of the treatment regimen to the end of that treatment regimen in study 8HA01EXT. The duration will stop and start for each treatment regimen change. If a subject is treated in a given treatment regimen more than once in study 8HA01EXT, the total durations in the same treatment regimen will be added together. For example, during study 8HA01EXT, if a subject is treated with the tailored prophylaxis regimen and then the weekly prophylaxis regimen and then goes back to the tailored prophylaxis regimen, then his total duration in the tailored prophylaxis regimen will be the sum of the two durations in the tailored prophylaxis regimen. Further details will be provided for individual analysis where needed.

The total duration of time allocated to each treatment regimen will be calculated in minutes and converted to days as the number of minutes divided by 1440.

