Treatment Regimens:	Treatment regimens are defined as follows: 
• On-Demand: all subjects enrolled in the trial and treated using an on-demand regimen• Prophylaxis: all subjects enrolled in the trial and treated using a tailored prophylaxis, weekly prophylaxis, or personalized prophylaxis regimen There will also be a surgery subgroup, which is defined as a subset of subjects from the prophylaxis and on-demand regimens who have major surgery during the course of the trial.
Duration of Treatment and Follow-up:	Subjects first dosed with rFVIII Fc when <12 years of age will be followed to at least 100 EDs, even if rFVIII Fc becomes commercially available. All subjects will have the opportunity to continue in this study for up to 4 years or until rFVIII Fc is commercially available in the applicable participating country.
Definition of Dose-Limiting Toxicity:	No dose-limiting toxicity for rFVIII Fc has been identified.
Statistical Methods:	In general, the data for subjects who enroll from the parent studies will have their data integrated with their data from 8HA01EXT. A parent study is defined as a study where subjects may be enrolled into 8HA01EXT after study completion or at a time specified in the protocol.

Demography and Baseline Disease Characteristics

The analysis of demography and baseline disease characteristics will be based on the Safety Analysis Set.

Demographics and baseline disease characteristics will be summarized categorically and/or with descriptive statistics, as appropriate, using the data at the entry of the parent studies.

Efficacy

Subjects who receive at least 1 dose of rFVIII Fc will be included in the Full Analysis Set (FAS). Efficacy analyses will be based on the FAS.

For subjects who have surgeries during the study, their efficacy data during the surgical period (including rehabilitation period) will be analyzed separately. The efficacy and surgical/rehabilitation periods will be defined in the statistical analysis plan for the purpose of determining the study periods during which data will be used for

CONFIDENTIAL

The information contained herein may not be used, disclosed, or published without the written consent of Biogen Idec MA Inc.

select efficacy analyses. Data on bleeding and rFVIII Fc consumption will be based on the efficacy period; surgical evaluations will be based on the surgical/rehabilitation period.

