5.3.2.1. Option 1: Tailored Prophylaxis

The Investigator may consider the following options for tailored prophylaxis to target a FVIII trough of up to 5%, but is encouraged to use the lowest effective dose targeting a FVIII trough

CONFIDENTIAL

The information contained herein may not be used, disclosed, or published without the written consent of Biogen Idec MA Inc.

level between 1% and 3%. If bleeding episodes occur at FVIII trough levels of 1% to 3%, further adjustments to dose or interval over the course of the study will target trough levels of up to 5%.

Dosing is approximately 25 IU/kg to 65 IU/kg every 3 to 5 days, or dosing 2 times per week at approximately 20 IU/kg to 65 IU/kg on Day 1 and 40 IU/kg to 65 IU/kg on Day 4. The dose and interval should be based on the subject's clinical profile observed in the preceding rFVIII Fc study, and/or his individual PK (if available), and FVIII trough and/or peak (recovery) values. In pediatric subjects, doses may be adjusted up to a maximum prophylactic dose of 80 IU/kg and the interval decreased to every 2 days, if necessary to maintain adequate FVIII activity trough levels and prevent spontaneous bleeding events.

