5.3.2.3. Option 3: Personalized Prophylaxis

If optimal prophylaxis dosing cannot be achieved using either of the above options, the Investigator may further personalize dosing to meet the needs of individual subjects.

The Investigator may consider the following personalized dosing options:

- Addition of "prevention" doses prior to strenuous activity.
- Targeting a FVIII trough level of >3%, if the bleeding history and/or activity level requires.
- Dosing less frequently.

The Investigator is not limited to the options above, and should consult the Medical Monitor for further consideration of a subject's dosing options. The personalized prophylaxis dosing option will require consultation with the Medical Monitor.

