7.1.4.3. Dose and/or Interval Modification Following Bleeding Episodes

Dose and/or interval modification following bleeding episodes can occur if a subject experiences ≥ 2 moderate or major spontaneous bleeding episodes over a rolling 8-week period. The Investigator can adjust the rFVIII Fc dose as follows:

- If an increase is required, the dose may be increased in increments of at least 5 IU/kg.
- The dose and/or interval may be adjusted after discussion with the Sponsor Medical Monitor.
- See Section [5.3](#) for description of regimen changes.

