16.4.3. Endpoints Analysis

16.4.3.1. Annualized Bleeding Episodes and Annualized rFVIIIIFc Consumption

Bleeding episodes will be annualized for each subject first, then summarized and tabulated by treatment arm, treatment regimen, or age cohort, as appropriate, in the parent studies, and by treatment regimen in 8HA01EXT. These analyses will also be performed for each type of bleed (spontaneous and traumatic). The number of spontaneous joint bleeding episodes and the consumption of rFVIIIIFc will be annualized in a similar fashion and tabulated.

Summaries of these data will be based on the FAS.

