5.1. General Principles

The following rules will be followed for all applicable analyses contained in this SAP, unless specified otherwise.

Because the subjects from studies 997HA301/997HA307/997HA309 and study 8HA02PED are in different age groups (i.e. ≥ 12 years of age for studies 997HA301/997HA307/997HA309 and < 12 years of age for study 8HA02PED) and may therefore have different safety and efficacy profiles, analyses will be performed separately for the groups of subjects from the parent study or parent studies combined, as described in the table below. Further, the table categories (i.e. age cohort, treatment regimen, etc) by type of analyses for each grouping are also detailed unless specified otherwise.

Groups of subjects from the parent study or parent studies combined	Categories by type of analyses
8HA02PED	Baseline/Concomitant therapy and procedures: Age cohort and overall; treatment regimen (including surgery subgroup) and overall Exposure: Age cohort and overall; treatment regimen and overall Efficacy: Age cohort; treatment regimen Patient-reported outcomes: Age cohort and overall; visit Compliance/surgery/Safety: Visit (if applicable)
997HA301 997HA301/997HA307/997HA309 combined	Baseline/Concomitant therapy and procedures: Treatment regimen (including surgery subgroup) and overall Exposure: Treatment regimen and overall Efficacy: Treatment regimen

	Patient-reported outcomes: Visit Compliance/surgery subgroup/Safety: Visit (if applicable)
Overall	Compliance/Surgery/Safety: Visit (if applicable)

Where treatment regimen (which is defined as treatment regimen in study 8HA01EXT) is:

- Tailored prophylaxis
- Weekly prophylaxis
- Personalized prophylaxis
- Episodic

Age cohort for subjects from study 8HA02PED is as reported for that study, namely:

- <6 years old
- 6 to <12 years old

Summaries of study 8HA01EXT data will be produced using standard summary statistics. Listings will also only include data from study 8HA01EXT and the treatment regimen associated with each data point, unless specified otherwise. Data collected at unscheduled visits will be included in the definition of the maximum and minimum post-baseline values.

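### For subjects from the studies in patients aged 12 or older, bleeding rate and consumption are planned only by four regimens that subjects can move between, partly because of bleeding; no summary covers each subject's whole time on prophylaxis

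*SAP*

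**What the plan says.** - SAP 5.3.1 analyses the regimen actually followed and splits a subject's time among regimens. A subject who changes "will appear in both the tailored prophylaxis and weekly prophylaxis regimens in the summaries based on the time he spent in the respective regimens".
- SAP 5.1 lists four regimens: tailored, weekly, personalized and episodic. For 997HA301 and for 997HA301/307/309 combined, the efficacy line reads "Efficacy: Treatment regimen". For 8HA02PED it reads "Efficacy: Age cohort; treatment regimen". The baseline and exposure lines add an overall category; the efficacy lines do not.
- SAP 6.5.4 determines consumption for each regimen. SAP 7.3.1 and the list of tables name no pooled prophylaxis row for ABR or consumption.
- SAP 6.5.5 does use an overall prophylaxis regimen for compliance, and SAP 6.5.1.2 pools tailored and weekly for the last prescribed dose.
- The protocol synopsis gives two treatment regimens, On-Demand and "Prophylaxis: all subjects enrolled in the trial and treated using a tailored prophylaxis, weekly prophylaxis, or personalized prophylaxis regimen". Protocol 16.4.3.1 asks for these endpoints by parent-study grouping "and by treatment regimen in 8HA01EXT".
- Protocol 7.1 lets subjects aged 12 or older change regimen, and Protocol 5.3 requires Sponsor Medical Monitor approval. One listed personalized option is "Targeting a FVIII trough level of >3%, if the bleeding history and/or activity level requires".
- Protocol 7.1.4.3 allows a dose or interval change after at least "2 moderate or major spontaneous bleeding episodes over a rolling 8-week period" and refers to Section 5.3 for regimen changes.

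**The concern.** The secondary objective includes prevention of bleeding. No hypothesis is tested, so the descriptive tables are the efficacy result. If some changes of regimen follow a run of bleeds, those bleeds stay in the regimen being left and the time after them goes to the new one. A subject whose bleeding tendency never changed can then look worse in one column and better in the next. More frequent bleeders may also collect in the regimen that receives switchers. In either case a regimen's ABR mixes the effect of the regimen with the reason for leaving or entering it, and one subject can sit in several columns.

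A per-subject rate over all prophylaxis time is not exposed to switches among the prophylaxis options. For the subjects from the studies in patients aged 12 or older, no such rate is planned.

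A smaller point concerns labels. Tailored prophylaxis is described as intended "to target a FVIII trough of up to 5" percent, while personalized prophylaxis may aim above 3%. A target between 3% and 5% fits both descriptions, so similar prescriptions could fall in different columns.

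**Working it through.** **The plan's own figure.** The only sample-size figure is a count: 144 + 50 + 12 + 8 = 214 in the SAP, and 144 + 50 = 194 in the protocol. Both reproduce. Neither is a power calculation, and this point does not depend on them.

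**How a segment is scored.** SAP 7.1.1 defines ABR = bleeds ÷ days in the efficacy period × 365.25, per subject. Subjects are then summarized with no stated weighting by time. SAP 5.3.2 requires two prophylactic injections but sets no minimum duration. SAP 5.3.1 starts a new prophylactic regimen at its first prophylactic dose and ends the previous one a minute earlier, so bleeds that prompted the change count in the old regimen. Short segments give extreme values:
- 2 bleeds in 56 days: 2 ÷ 56 × 365.25 = 13.0
- 1 bleed in 3 days: 1 ÷ 3 × 365.25 = 121.75

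**Simulation.** There were 40,000 subjects per setting, followed for 4 years (the planned maximum), with no true difference between regimens. A subject may switch once, at the second of two bleeds no more than 56 days apart, if at least 14 days remain. The following are assumptions, not in the documents: the true mean ABR; whether subjects share one rate or vary (gamma, shape 1); the share of triggered subjects who switch; and that every bleed counts toward the trigger.

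Results for a true mean ABR of 2:

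| Subjects' rates | Triggered subjects who switch | First column, mean (median) | Second column, mean (median) | All prophylaxis time per subject, mean | Total bleeds ÷ person-years, first / second |
|---|---|---|---|---|---|
| Equal | 100% | 3.91 (2.36) | 2.00 (1.91) | 2.00 | 2.01 / 2.00 |
| Equal | 25% | 2.49 (2.00) | 2.00 (1.92) | 2.00 | 2.00 / 2.00 |
| Varying | 100% | 3.99 (1.55) | 3.09 (2.58) | 2.01 | 1.12 / 3.44 |
| Varying | 25% | 2.46 (1.31) | 3.11 (2.63) | 1.99 | 1.83 / 3.46 |

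At other equal true rates, the first column's mean was 1.68 (100% switching) or 1.17 (25%) for a rate of 1, and 8.49 or 5.04 for a rate of 4.

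**Reading the table.**
1. With equal rates, the excess comes from averaging unweighted ABRs over segments that end at a bleed. Total bleeds over person-time stay at about 2.0 in both columns.
2. When subjects differ, selection is added: higher-rate subjects move to the second column. The difference in means is 3.99 against 3.09 at 100% switching and reverses to 2.46 against 3.11 at 25%. Person-time rates do not remove this part.
3. The rate over all prophylaxis time stays at about 2.0 in every row.

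Switches to or from the episodic regimen were not simulated, and neither was consumption.

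**The case against.** The strongest reply is that nothing here breaches the protocol. The pooled definition stands in the synopsis, which calls itself a brief summary. The body of the protocol (5.3, 7.1, 10.1) speaks of four regimens, and 16.4.3.1 asks only for a breakdown by regimen. That stands: four columns are legitimate, and a reader who infers a departure from the protocol goes too far. What remains is that the protocol names a pooled Prophylaxis regimen and the SAP gives it no ABR or consumption summary, although it pools prophylaxis for compliance.

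Four further inferences are tempting but not supported:
- **That every group lacks a pooled view.** 8HA02PED efficacy is also by age cohort. If the semicolon in SAP 5.1 separates two breakdowns, as the neighbouring lines suggest, that table pools tailored and personalized time, the only regimens open to subjects under 12.
- **That subjects switch freely, or that the 8-week rule moves them.** Changes need Medical Monitor approval. The rule governs dose and interval and only points to regimen changes, and tailored prophylaxis allows adjustment after bleeds within itself. Personalized options also include less frequent dosing and doses before activity, which need not follow bleeding.
- **That the bias has a known direction, or shrinks in proportion to the share switching.** The last two rows of the table contradict this.
- **That regimen labels depend on the site.** The trough targets overlap, but personalized prophylaxis applies only when the other options do not achieve optimal dosing, and regimen changes are recorded on the eCRF.

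The SAP is open about switchers appearing in more than one regimen. It also tabulates regimen changes, reports total subject-years and lists per-subject bleeding endpoints. These help a careful reader but do not replace a summary.

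**Conclusion.** The gap is real and limited. For subjects from 997HA301 and from 997HA301/307/309 combined, the plan gives no ABR or consumption over each subject's whole prophylaxis time, and the regimen columns it does give can be distorted by bleed-related changes. With equal true rates of 2, the first column's mean was 2.5 to 3.9 in simulation as the share of triggered subjects switching rose from 25% to 100%, and its median moved only from 2.0 to 2.4. These figures illustrate the mechanism and do not estimate the bias in this study. The documents do not say what share of switches follows bleeding, the simulation counts every bleed toward the trigger where the protocol requires moderate or major spontaneous ones, and the direction can reverse when subjects differ.

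No test or error rate is affected. A pooled column would not be proof against all switching, as a reader might infer: moves between prophylaxis and episodic treatment would still affect it.

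**What to change.** 1. In SAP 5.1, 6.5.4 and 7.3.1, add an any-prophylaxis column for each parent-study group: one ABR (all bleeds, spontaneous, spontaneous joint) and one annualized consumption per subject over all his prophylaxis efficacy time.
2. For 8HA02PED, state that the age-cohort table pools prophylaxis time, or add the same column there.
3. Keep the tailored, weekly and personalized columns, described as descriptive with switchers counted in each. Show total bleeds over total person-time beside the per-subject means. This exposes the short-segment effect but not selection.
4. If switches between prophylaxis and episodic treatment prove common, add ABR by starting regimen.
5. Reconcile the trough-target wording for tailored and personalized prophylaxis (Protocol 5.3.2.1 and 5.3.2.3) so that each prescription maps to one label. No target is proposed here.

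The cost is one column from data already derived, plus person-time rates from the same counts. The drawback is that the pooled column mixes dosing intensities, which is why the regimen columns stay beside it.
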